10. PHARMACOVIGILANCE

The Investigator is responsible for the detection and documentation of events meeting the criteria and definitions detailed below.

Full details of contraindications and side effects that have been reported following administration of the IMP can be found in the relevant Summary of Product Characteristics (SPC) Booklet for cilostazol and isosorbide mononitrate.

Participants will be instructed to contact their Investigator at any time after being randomised if any symptoms develop. All adverse events (AE) that occur after randomisation until death or completion of active trial follow-up (two weeks after the last dose of IMP is administrated) must be recorded in the Case Report Form (CRF) or AE log. In the case of an AE, the Investigator should initiate the appropriate treatment according to their medical judgment.

The main factor in assessing the safety of cilostazol and isosorbide mononitrate is the collection of the trial secondary outcomes:

- recurrent ischaemic stroke
- TIA
- major systemic or brain haemorrhage
- fatal or non-fatal MI
- death of any cause
- dementia.

These outcomes should be reported as trial outcomes in the e-CRF and are exempt from the safety reporting as SAEs. Any other adverse events that fulfil the seriousness criteria of the adverse event should be reported as SAE to the Sponsor.

Both cilostazol and isosorbide mononitrate have a known safety profile. The IMP symptoms that are not serious adverse reactions (AR), such as headache or loose stools, will be collected and reported on the e-CRF at each follow-up visit. The SARs and SUSARs will be reported to the Sponsor.

CR007-T01 v9.0 Page **50** of **67**

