2.2.2 Secondary Endpoints

At 18 months:

- dependency (defined as mRS>2)
- tMOCA
- TICS
- Concentration (from MMSE)
- Animal naming
- Recurrent ischaemic stroke or TIA or haemorrhagic stroke
- Fatal or non-fatal MI
- Stroke Impact Scale (individual domains and global)
- EQ5D-5L, EQ-VAS
- Death, due to vascular and any cause;
- Safety SAEs;
- IMP Symptoms (headache; palpitations; loose stools; falls; etc);
- Composite of recurrent stroke or TIA, MI, death, dependency (mRS>2), cognitive impairment.
- Global Clinical Outcome of recurrent stroke or TIA, MI, death, mRS>2, cognitive impairment, QoL, mood (ZUNG)
- Health economic usage

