reported events may come from several sources (site research team, participant, follow-up questionnaire, GP or carer, friend, or relative). The relevant clinical, radiographic or pathological information about the reported event will be obtained from the site hospital research team, e.g., Outpatient clinic letter, Discharge summary, brain imaging and radiological report, and blood results. Patient identifiers will be redacted from these documents before sending for internal adjudication to confirm if the event is classified as the outcome. Any potential SAEs or SUSARS identified during the review process will be reported to the sponsor using online e-CRF.

The anonymised **brain scans** that diagnosed the qualifying lacunar stroke and any reported clinical outcomes will be stored in a separate imaging database described in section 8.3. The central research staff will check each brain scan to confirm that it relates to the correct participant, correct time of the event, includes the required imaging sequences, does not show other explanations for the symptoms and will make scan available for the readers.

All case report forms must be reviewed and approved by the ACCORD Monitor prior to use (see ACCORD SOP CR013 CRF Design and Implementation).

NOTE: All electronic case report forms are subject to Co-Sponsor approval (see section 8.3).

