10.4.3 Assessment of Expectedness

If the event is an AR the evaluation of expectedness will be made based on knowledge of the reaction and the relevant product information documented in the SPC Booklet. – section 4.8 of the document where the info can be found. The event may be classed as either:

- Expected: the AR is consistent with the toxicity of the IMP listed in the SPC Booklet.
- **Unexpected**: the AR is not consistent with the toxicity in the SPC Booklet.

Fatal and life threatening SARs should usually be considered unexpected. Fatal SARs can only be expected for IMPs with an MA in the EU, when it is clearly stated in the list of ARs of the SPC (Section 4.8) that the IMP causes fatal SARs.

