10.6 REPORTING OF SAEs/SARs/SUSARs

Once the Investigator becomes aware that an SAE has occurred in a study participant, the information will be reported to the ACCORD Research Governance **within 24 hours**. If the Investigator does not have all information regarding an SAE, they should not wait for this additional information before notifying ACCORD. The SAE report form can be updated when the additional information is received.

The SAE report will provide an assessment of causality and expectedness at the time of the initial report to ACCORD according to Sections 11.4.2, Assessment of Causality and 11.4.3, Assessment of Expectedness.

The SAE form will be transmitted via email to [contact]. Only forms in a pdf format will be accepted by ACCORD via email. Forms may also be submitted by hand to the office. Where missing information has not been sent to ACCORD after an initial report, ACCORD will contact the Investigator and request the missing information. The Investigator must respond to these requests in a timely manner.

The SAEs, which are defined as secondary outcomes (section 11), will be captured as endpoint data on e-CRF and not reported to the sponsor as SAEs.

All reports sent to ACCORD and any follow up information will be retained by the Investigator in the Investigator Site File (ISF).

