10.7 REGULATORY REPORTING REQUIREMENTS

ACCORD is responsible for pharmacovigilance reporting on behalf of the Co-Sponsors (The University of Edinburgh and NHS Lothian).

ACCORD has a legal responsibility to notify the regulatory competent authority and relevant ethics committee (Research Ethics Committee (REC) that approved the trial) of SUSARS. Fatal or life threatening SUSARs will be reported no later than 7 calendar days and all other SUSARs will be reported no later than 15 calendar days after ACCORD is first aware of the reaction.

ACCORD (or delegate) will inform Investigators at participating sites of all SUSARs and any other arising safety information.

ACCORD will be responsible for providing safety line listings and assistance; however, it is the responsibility of the Investigator to prepare the Development Safety Update Report. This annual report lists all SARs and SUSARs reported during that time period. The responsibility

of submitting the Development Safety Update Report to the regulatory authority and RECs, lies with ACCORD.

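### Outcome events are exempt from SAE reporting even when trial drug is suspected, and this is not reconciled with the SAR/SUSAR duty or given a deadline

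*Protocol*

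**What the plan says.** The opening of Protocol section 10 lists the outcomes it treats as the main safety measure: recurrent ischaemic stroke, TIA, "major systemic or brain haemorrhage", "fatal or non-fatal MI", death from any cause, and dementia. It continues: "These outcomes should be reported as trial outcomes in the e-CRF and are exempt from the safety reporting as SAEs". Section 10.6 says the same of SAEs that are secondary outcomes: they "will be captured as endpoint data on e-CRF and not reported to the sponsor as SAEs". Neither sentence depends on suspected cause.

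Other parts of the Protocol bear on the same events:

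- Section 10.3 has the investigator complete an SAE form whenever an adverse event is serious, with no exclusion for outcomes.
- Section 10.4 requires each adverse event to be assessed for seriousness, causality and severity, and each adverse reaction for expectedness.
- Section 6.8 and the end of the introduction to section 10 say that SARs and SUSARs go to the sponsor.
- Section 10.4.3: "Fatal and life threatening SARs should usually be considered unexpected".
- Section 10.7: "Fatal or life threatening SUSARs will be reported no later than 7 calendar days". Other SUSARs have 15 days. Both periods run from the sponsor office's first awareness.
- Section 7.2, on the review of outcome events: "Any potential SAEs or SUSARS identified during the review process will be reported to the sponsor using online e-CRF". It gives no time limit.

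**The concern.** Exempting expected endpoint events from expedited SAE reporting is ordinary practice in an outcome trial. It is normally paired with a statement of what happens when such an event is thought to be due to the study drug. That statement is absent here, and the exempt list contains the events for which it matters most: serious bleeding, MI and death. Intracerebral haemorrhage, systemic bleeding and fatal SAEs are also the events named in the DMC harm guideline in section 3.

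What is at stake is whether, and when, the sponsor learns of a suspected drug-related bleed or death. The sponsor's statutory reporting depends on that awareness. A secondary issue is whether all sites send the same event down the same path.

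**Working it through.** No arithmetic applies. The check follows one hypothetical event through the text: a fatal systemic bleed in a participant allocated cilostazol, which the site investigator judges possibly related.

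1. **Classification.** Under 10.1 the bleed is an adverse event and is serious because it resulted in death. Judged possibly related under 10.4.2, it is a serious adverse reaction. Under 10.4.3 a fatal reaction is usually, not always, unexpected, so it would usually be a SUSAR.

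2. **Site instruction.** Section 10.3 says to complete the SAE form. Sections 10 and 10.6 say this event is not reported to the sponsor as an SAE. The end of the section 10 introduction and section 6.8 say that SARs and SUSARs are reported to the sponsor. No sentence ranks these instructions.

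3. **Causality.** The assessment is required by 10.4 whichever instruction is followed. What is missing is its transmission: 10.6 makes the SAE report the vehicle that carries causality and expectedness to the sponsor, and the exemption removes that report.

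4. **Deadline.** The only timed step from investigator to sponsor for these events is the 24 hours in 10.6, and it starts from awareness of an SAE. The SAR/SUSAR sentences in 6.8 and 10 carry no time limit of their own.

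5. **Backstop.** Section 7.2 has members of the trial management group review outcome events, using clinical documents with patient identifiers removed. The stated aim is to remove duplicates and confirm that the event qualifies as an outcome. Potential SUSARs found there are passed on, but no period is fixed for the review or the onward report.

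6. **Regulatory clock.** The 7- and 15-day limits in 10.7 start when the sponsor office first becomes aware. If the site follows the exemption literally, nothing in the text fixes when that happens.

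**The exempt list.** Section 10.6 defines the exempt events as secondary outcomes and refers to section 11, which is trial management. Section 10.4.1 cites 11.1 for the definitions in 10.1, and 10.6 cites 11.4.2 and 11.4.3 for text numbered 10.4.2 and 10.4.3. The reference is therefore stale numbering for section 10. A real mismatch remains. Section 2.2.2 lists "Recurrent ischaemic stroke or TIA or haemorrhagic stroke", MI and death as secondary endpoints, but not major systemic haemorrhage or dementia, both of which section 10 exempts as secondary outcomes. Section 1.1 reports that all four LACI-2 haemorrhages were systemic, although it does not say they were major or drug-related.

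**The case against.** The strongest reply is that the exemption is only from reporting an event as an SAE. It does not switch off the rest of section 10. An outcome event is still an adverse event. Sections 10.3 and 10.4 require its causality to be recorded and assessed, sections 6.8 and 10 require SARs and SUSARs to reach the sponsor, and 7.2 adds a second check. The annual safety report described in 10.7 covers SARs and SUSARs and excludes no outcome events. The DMC sees unblinded data, and section 9.2 analyses deaths and systemic haemorrhage by arm. The section 10 list is explicit, and section 6.9 and the footnotes to the study assessments table name the same events.

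Most of this stands, and it rules out three stronger readings:

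- A reader might infer that exempt events need no causality assessment. Section 10.4 says the opposite.
- A reader might infer that a drug-related fatal bleed necessarily bypasses the SUSAR route and the annual report. The duty to report SARs and SUSARs is stated without an outcome exclusion, so omission is possible but not directed.
- A reader might scale LACI-2's four haemorrhages and four deaths to 1300 participants and call the result the number of events affected. Those are counts whatever the cause, and the gap concerns only suspected drug-related events. Section 1.1 describes only two LACI-2 SAEs as possibly related to either drug.

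The reply does not supply a deadline for an exempt event, and it does not remove the conflict between 10.3 and the exemption in 10 and 10.6.

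**Conclusion.** The point holds as an unresolved conflict between stated rules. Sections 10 and 10.6 remove outcome events from SAE reporting without regard to suspected cause. Section 10.3 and the SAR/SUSAR duty in 6.8 and 10 point the other way. The only timed site-to-sponsor route for these events is attached to the report that the exemption removes. Followed literally, the text can delay or prevent sponsor awareness of a suspected drug-related bleed or death, and so delay the start of the 7- or 15-day clock.

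The size cannot be put as a number from the Protocol. The affected events are the subset of outcomes judged possibly related, probably few, but they include the gravest. The conclusion rests on the Protocol wording alone. A safety reporting manual or an eCRF not shown here could already close the gap in practice, in which case the Protocol should say so. The mismatch between the section 10 list and 2.2.2 is minor and editorial, but it bears on routing because 10.6 defines the exemption by secondary-outcome status.

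**What to change.** Reconcile sections 6.8, 7.2, 10, 10.3 and 10.6 as follows:

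- State in 10 and 10.6 that the exemption applies only to outcome events the site investigator judges unrelated to trial drug.
- Record that judgement on the outcome eCRF, so that the assessment already required by 10.4 is visible for each outcome event.
- State that any outcome event judged possibly related goes through the 10.6 route within 24 hours, with causality and expectedness.
- Amend 10.3 so that its SAE-form instruction matches.
- Replace the reference to section 11 in 10.6 with the explicit list in section 10, and bring 2.2.2 into agreement by dealing with major systemic haemorrhage and dementia.

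The cost is one eCRF field, a few sentences of amendment, and an extra SAE form for the small number of outcome events judged possibly related. The efficacy analysis and sample size do not change.

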10.1 DEFINITIONS

An **adverse event** (AE) is any untoward medical occurrence in a clinical trial participant which does not necessarily have a causal relationship with an investigational medicinal product (IMP).

An **adverse reaction** (AR) is any untoward and unintended response to an IMP which is related to any dose administered to that participant.

A serious adverse event (SAE), serious adverse reaction (SAR). Any AE or AR that at any dose:

- results in death of the clinical trial participant;
- is life threatening*;
- requires in-patient hospitalisation^ or prolongation of existing hospitalisation;
- results in persistent or significant disability or incapacity;
- consists of a congenital anomaly or birth defect;
- results in any other significant medical event not meeting the criteria above.

*Life-threatening in the definition of an SAE or SAR refers to an event where the participant was at risk of death at the time of the event. It does not refer to an event which hypothetically might have caused death if it were more severe.

^Any hospitalisation that was planned prior to enrolment will not meet SAE criteria. Any hospitalisation that is planned post enrolment will meet the SAE criteria.

A suspected unexpected serious adverse reaction (SUSAR) is any AR that is classified as serious and is suspected to be related to the IMP, that it is not consistent with the information about the IMP in the Summary of Product Characteristics (SPC) booklet or Investigators Brochure.

10.2 IDENTIFYING AES AND SAES

Participants will be asked about the occurrence of AEs/SAEs at every visit during the study. Open-ended and non-leading verbal questioning of the participant will be used to enquire about AE/SAE occurrence. Participants will also be asked if they have been admitted to hospital, had any accidents, used any new medicines or changed concomitant medication regimens. If there is any doubt as to whether a clinical observation is an AE, the event will be recorded.

AEs and SAEs may also be identified via information from support departments e.g. laboratories.

10.3 RECORDING AEs AND SAEs

When an AE/SAE occurs, it is the responsibility of the Investigator, or another suitably qualified physician in the research team who is delegated to record and report AEs/SAEs, to review all documentation (e.g. hospital notes, laboratory and diagnostic reports) related to the event. The Investigator will then record all relevant information in the CRF/AE log and on the SAE form (if the AE meets the criteria of serious).

Information to be collected includes dose, type of event, onset date, Investigator assessment of severity and causality, date of resolution as well as treatment required, investigations needed and outcome.

10.3.1 Pre-existing Medical Conditions

Pre-existing medical conditions (i.e. existed prior to informed consent) should be recorded as medical history and only recorded as adverse events if medically judged to have worsened during the study.

10.3.2 Worsening of the Underlying Condition during the Trial

Medical occurrences or symptoms of deterioration that are expected due to the participant's underlying condition should be recorded in the patient's medical notes and only be recorded as AEs on the AE log if medically judged to have unexpectedly worsened during the study. Events that are consistent with the expected progression of the underlying disease should not be recorded as AEs.

Adverse events that are not outcome events, SAEs, SARs, and SUSARs and align with the anticipated progression of the underlying disease should not be recorded or reported, including:

- Consequences of lacunar stroke
- Consequences of outcome events that happen during trial follow-up
- Consequences of pre-existing co-morbidities at the time of consent or during the trial follow-up.

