10.5 RECORDING OF AEs

All adverse events for each participant will be recorded on the AE log.

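### Section 10.3.2 contradicts itself on whether a serious event that fits expected disease progression is recorded, and unblinded site physicians make that judgement

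*Protocol*

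**What the plan says.** The general rule is to record. The opening of section 10 says that all AEs from randomisation until two weeks after the last dose "must be recorded in the Case Report Form (CRF) or AE log". It lists outcomes exempt from SAE reporting (recurrent ischaemic stroke, TIA, major haemorrhage, MI, death, dementia) and requires any other adverse event that meets a seriousness criterion to go to the sponsor as an SAE. Section 10.5 repeats: "All adverse events for each participant will be recorded on the AE log". Section 10.2 adds: "If there is any doubt as to whether a clinical observation is an AE, the event will be recorded".

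Section 10.3.2 then carves out disease progression, twice. The first paragraph admits deterioration due to the underlying condition to the AE log only if it worsened unexpectedly, and ends: "Events that are consistent with the expected progression of the underlying disease should not be recorded as AEs". The second paragraph is narrower: "Adverse events that are not outcome events, SAEs, SARs, and SUSARs and align with the anticipated progression of the underlying disease should not be recorded". A list of three examples follows it.

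Section 10.1 defines an SAE as an AE or AR that meets one of the listed seriousness criteria. Under 10.4, the principal investigator or a delegated site physician assesses seriousness, causality and severity. Section 5.5.1 says the trial is open label and that site staff know the allocation. SAEs are a secondary endpoint (2.2.2), analysed by binary logistic regression on events that meet the protocol's definitions (9.2).

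**The concern.** The two paragraphs of 10.3.2 give different answers for the same event. Take a participant admitted to hospital because walking has deteriorated. The second paragraph keeps the event, because it is serious. The first removes it if the physician thinks the decline was to be expected. Seriousness plays no part in the first paragraph's test.

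Two things are at stake. The SAE endpoint is defined by reference to the protocol's own definitions, so a contradiction there leaves the edge of the endpoint undefined, and the person who settles it knows the treatment. Under-recording could then differ between arms in either direction. Also, an event that is never recorded is never assessed for causality, so a possible SAR or SUSAR could be missed. Section 10.4.2 already gives the natural history of the disease a proper place, as one of the alternative causes weighed when causality is judged. The first paragraph of 10.3.2 moves that judgement ahead of recording.

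**Working it through.** The protocol states no figure on this point, so there is none to reproduce. The check is a comparison of texts for one case: an event that meets a seriousness criterion, is not a listed outcome, and fits expected progression.

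| Place | What it implies for this event |
|---|---|
| 10, opening | Recorded, and reported to the sponsor as an SAE |
| 10.1 | An SAE only if it is first an AE or AR |
| 10.3.2, first paragraph | Not recorded as an AE |
| 10.3.2, second paragraph | Outside the exemption, because it is an SAE |
| 10.5 | Recorded on the AE log |
| 10.4.1 | Assess seriousness using Section 11.1 |

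1. The first paragraph of 10.3.2 conflicts with the second, with the opening of section 10 and with 10.5.
2. Through the definition in 10.1, an event kept off the AE record need never reach the SAE form.
3. The pointer in 10.4.1 does not help. Section 11.1 describes the Trial Management Group; the seriousness criteria are in 10.1. Section 10.6 has the same numbering slip: it sends causality and expectedness to 11.4.2 and 11.4.3, but they are in 10.4.2 and 10.4.3.

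Neighbouring texts, checked for the same fault:

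- Co-morbidities. Section 10.3.1 says pre-existing conditions are "only recorded as adverse events if medically judged to have worsened during the study". The third example in 10.3.2 exempts "Consequences of pre-existing co-morbidities at the time of consent or during the trial follow-up". The two pull apart, but the example sits under the second paragraph, which excludes SAEs. The direct clash is confined to non-serious AEs.
- Planned admissions. Section 10.1 says an admission planned before enrolment is not an SAE, and: "Any hospitalisation that is planned post enrolment will meet the SAE criteria". These two rules are consistent with each other. What is left unclear is an admission planned after enrolment for a pre-existing condition that has not worsened, which 10.3.1 would not call an AE.

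A sense of scale, on assumed rates only. Let p be the true SAE risk in both arms, u the share of one arm's SAEs left unrecorded, and n = 650 per comparison group (9.1). The recorded risks are p and p(1 − u). The chance of a false significant difference in the direction of the omission is about Φ(p·u/SE − 1.96), with SE = √{[p(1 − p) + p(1 − u)(1 − p(1 − u))]/n}; its nominal value is 2.5%.

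With p = 10% and u = 10%: recorded risks 10% and 9%; OR = (0.09/0.91)/(0.10/0.90) = 0.89; SE = √[(0.0900 + 0.0819)/650] = 0.0163; Φ(0.615 − 1.96) = 8.9%.

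| u (assumed) | OR, p from 10% to 30% | False significance in that direction |
|---|---|---|
| 5% | 0.95 to 0.93 | 5% to 9% |
| 10% | 0.89 to 0.86 | 9% to 22% |
| 20% | 0.78 to 0.74 | 24% to 68% |

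The protocol supports no particular row. Here u is the share of SAEs that could be called progression multiplied by the share of those dropped in one arm beyond the other, and neither is given.

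**The case against.** The best reply is that the rule for serious events is already there. The opening of section 10 requires any other serious adverse event to be reported, 10.6 sets a 24-hour limit and excepts only outcome events, and the second paragraph of 10.3.2 takes SAEs out of the exemption. On this view 10.3.2 is only a recording rule: it leaves the broad AE definition in 10.1 untouched, so a serious event remains an SAE. There are also further routes to capture. Masked central co-ordinators record and report SAEs as well as sites, drawing on questionnaires and hospital-record alerts (5.5.1, 6.8). Participants are asked about hospital admissions at every visit (10.2). The trial management group's event review forwards potential SAEs (7.2). The chief investigator may upgrade but not downgrade an event (10.4). Falls are also collected separately on the masked central questionnaires at 6, 12 and 18 months.

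Much of this stands, and it limits the point. It does not remove it. The bar on downgrading protects only events that a site has already called SAEs. The record-if-in-doubt rule in 10.2 asks whether an observation is an AE, and the first paragraph of 10.3.2 tells the physician not to record it as one. Central staff may report an event, but the medical assessment rests with the site investigator or delegate.

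A reader might infer that section 10 gives opposite rules on three separate topics. The text does not support that. The two planned-admission sentences agree with each other, the co-morbidity example excludes serious events, and 10.2 is a tie-breaker towards recording rather than a further contradiction.

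**Conclusion.** The contradiction is real and is confined to the first paragraph of 10.3.2 as it applies to serious events other than the listed outcomes. It leaves the boundary of a secondary safety endpoint, and entry to causality assessment, open to a judgement made with knowledge of allocation. The primary endpoint is unaffected, and the listed outcomes are captured separately.

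A reader might go further and conclude that the SAE comparison will be biased by some stated amount. The protocol does not support that. It gives no SAE rate for this trial, its background section reports few SAEs in LACI-2, and nothing indicates how many serious events would be called progression or that sites would do so differently by arm. The figures above show only that modest differential omission could matter. The conclusion rests on the wording alone and on one assumption: that a site might follow the first paragraph literally.

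**What to change.** - In 10.3.2, restrict the first paragraph to non-serious events.
- Add a sentence: any event that meets a seriousness criterion in 10.1, other than the listed trial outcomes, is recorded and reported as an SAE, and disease progression is considered only when causality is assessed.
- In 10.4.1, correct the pointer from Section 11.1 to 10.1, and check the similar pointers in 10.6.
- Reconcile the wording of 10.1 (admissions planned after enrolment), 10.3.1, the third example in 10.3.2, and 10.5, so that each states the same carve-outs.

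The fix should not exclude planned admissions for unworsened conditions from the SAE analysis. That would make another unblinded judgement decide what is counted.

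The cost is a few sentences of protocol text and a few more SAE forms for progression-type admissions. Sample size, visits and the primary analysis do not change.
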